**Table 13: Operating Characteristics for the Integrated Bayesian Futility Analysis Under the Global Null Hypothesis**

Integrated Bayesian Analysis			18 Simon 2-Stage Designs	
Expected Sample Size	Probability of at Least 1 False Positive	Expected Number of False Rejections	Expected Sample Size	Expected Number of False Rejections
355.2	0.0876	0.104	457.2	0.9

## 9.2. Data Cutoff for Interim Analysis

As discussed in Section 9.1.1, the DMC will meet every 6 months to review safety analyses. All efficacy and safety analyses will use a clinical data cutoff of 3 weeks before execution of the planned safety or interim analysis. This period will help ensure accuracy of the interim data by providing the sponsor time to perform data review, issue queries regarding data quality issues to sites, and to resolve such queries.

As per Section 9.1.2.2, the IRT system will use the number of responses and number of evaluable subjects in each cohort to perform the pooled PoS1 and PoS2 calculations for futility whenever a subject with endometrial, gastric, or head and neck cancer enters screening. To perform quality control checks of the futility analysis within the IRT system, the sponsor will review the disease response data within the IRT system for consistency with the clinical database and request changes to resolve discrepancies. There will be periodic data extracts to identify discrepancies between the IRT system and the clinical database.

## 10. CHANGES AND MODIFICATIONS TO THE ANALYSIS PLAN

All versions of the SAP are listed in Table 14.

**Table 14: Statistical Analysis Plan Versions**

SAP Version	Date
Original	05 DEC 2017

### 10.1. Changes to Protocol-Defined Analyses

Not applicable.

### 10.2. Changes to the Statistical Analysis Plan

Not applicable.

## APPENDIX A. PLANNED TABLES AND FIGURES

This appendix provides a list of the planned tables and figures for the Clinical Study Report. Standard tables will follow the conventions in the Standard Safety Tables initial version. Shells are provided for nonstandard tables in a separate document. In-text tables are identical in structure and content as appendix tables, but follow a Rich Text Format.

The list of tables, figures, and the shells are to be used as guideline. Modifications of the list or shells that do not otherwise affect the nature of the analysis will not warrant an amendment to the SAP.

### Tables

Table No.	Title	Population	Standard	In-Text
1.1 Baseline and Demographic Characteristics				
1.1	Disposition			
1.1.1.1	Analysis Populations	Phase 1 FAS Population	X	X
1.1.1.2	Analysis Populations	Phase 2 FAS Population	X	X
1.1.2.1	Summary of Subject Disposition	Phase 1 FAS Population	X	X
1.1.2.2	Summary of Subject Disposition	Phase 2 FAS Population	X	X
1.1.2.3	Summary of Subject Disposition	FAS Population	X	
1.1.3.1	Summary of Number of Subjects Enrolled by Country and Site	Phase 1 FAS Population	X	
1.1.3.2	Summary of Number of Subjects Enrolled by Country and Site	Phase 2 FAS Population	X	
1.2 Demography				
1.2.1	Summary of Demographics	Phase 1 FAS Population	X	X
1.2.2	Summary of Demographics - by Tumor Type	Phase 2 FAS Population	X	X
1.3 Baseline Characteristics				
1.3.1.1	Summary of Baseline Disease Characteristics and Disease History for Phase 1 Solid Tumor Types	Phase 1 FAS Population		
1.3.2.1	Summary of Baseline Disease Characteristics and Disease History for Phase 2 Solid Tumor Types	Phase 2 Biopsy FAS Population		
1.3.2.2	Summary of Baseline Disease Characteristics and Disease History	Phase 2 Endometrium FAS Population		
1.3.2.3	Summary of Baseline Disease Characteristics and Disease History	Phase 2 Gastric FAS Population		
1.3.2.4	Summary of Baseline Disease Characteristics and Disease History	Phase 2 SCCHN FAS Population		

Table No.	Title	Population	Standard	In-Text
1.4 Prior Medication and Concomitant Medication				
1.4.1.1	Summary of Prior Systemic Therapy	Phase 1 FAS Population		
1.4.1.2	Summary of Prior Systemic Therapy - by Tumor Type	Phase 2 FAS Population		
1.4.2.1	Summary of Prior Medications	Phase 1 FAS Population		
1.4.2.2	Summary of Prior Medications - by Tumor Type	Phase 2 FAS Population		
1.4.3.1	Summary of Concomitant Medications	Phase 1 FAS Population	X	
1.4.3.2	Summary of Concomitant Medications - by Tumor Type	Phase 2 FAS Population	X	
1.5 Others				
1.5.1	Summary of General Medical History	Phase 1 FAS Population	X	
1.5.2	Summary of General Medical History - by Tumor Type	Phase 2 FAS Population	X	
1.5.3	Summary of Protocol Deviations	FAS Population		
2 Efficacy				
2.1.1.1	Summary of Confirmed Best Response, Duration of Response, and Duration of Disease Control Under RECIST v1.1 - by Treatment Group and Tumor Type	Phase 2 Response Evaluable Population		X
2.1.1.2	Summary of Unconfirmed Best Response Under RECIST v1.1 - by Treatment Group and Tumor Type	Phase 2 Response Population		X
2.2.1	Summary of Unconfirmed Best Response, Duration of Response, and Duration of Disease Control Under RECIST v1.1 - by Treatment Group and Dose	Phase 1 Response Evaluable Population		X
2.2.2	Summary of Unconfirmed Best Response, Duration of Response, and Duration of Disease Control Under mRECIST v1.1 - by Treatment Group and Dose	Phase 1 Response Evaluable Population		X
2.2.3.1	Summary of Confirmed Best Response, Duration of Response, and Duration of Disease Control Under mRECIST v1.1 - by Treatment Group and Tumor Type	Phase 2 Response Evaluable Population		X
2.2.3.2	Summary of Unconfirmed Best Response Under mRECIST v1.1 - by Treatment Group and Tumor Type	Phase 2 Response Evaluable Population		X
2.4.1	Summary of Progression-Free Survival Under RECIST v1.1	Phase 1 FAS Population		X
2.4.2	Summary of Progression-Free Survival Under RECIST v1.1 - by Tumor Type	Phase 2 FAS Population		X
2.5.1	Summary of Progression-Free Survival Under mRECIST v1.1	Phase 1 FAS Population		X
2.5.2	Summary of Progression-Free Survival Under mRECIST v1.1 - by Tumor Type	Phase 2 FAS Population		X
2.6.1	Summary of Overall Survival	Phase 1 FAS Population		X
2.6.2	Summary of Overall Survival - by Tumor Type	Phase 2 FAS Population		X

Table No.	Title	Population	Standard	In-Text
Safety				
3.1 Dose Exposure				
3.1.1.1	Summary of Drug Exposure to INCAGN01876 - by Treatment Group and Dose	Phase 1 FAS INCAGN01876 Population		X
3.1.1.2	Summary of Drug Exposure to INCAGN01876 - by Treatment Group and Tumor Type	Phase 2 FAS INCAGN01876 Population		X
3.1.2.1	Summary of Drug Exposure to Nivolumab - by Treatment Group and Dose	Phase 1 FAS Fixed Nivolumab Population		X
3.1.2.2	Summary of Drug Exposure to Nivolumab - by Treatment Group and Dose	Phase 1 FAS Weighted Nivolumab Population		X
3.1.2.3	Summary of Drug Exposure to Nivolumab - by Treatment Group and Tumor Type	Phase 2 FAS Fixed Nivolumab Population		X
3.1.2.4	Summary of Drug Exposure to Nivolumab - by Treatment Group and Tumor Type	Phase 2 FAS Weighted Nivolumab Population		X
3.1.3.1	Summary of Drug Exposure to Ipilimumab - by Treatment Group and Dose	Phase 1 FAS Ipilimumab Population		X
3.1.3.2	Summary of Drug Exposure to Ipilimumab - by Treatment Group and Tumor Type	Phase 2 FAS Ipilimumab Population		X
3.1.4.1	Summary of Drug Exposure to INCAGN01876 by Visit - by Treatment Group and Dose	Phase 1 FAS INCAGN01876 Population		
3.1.4.2	Summary of Drug Exposure to INCAGN01876 by Visit - by Treatment Group and Tumor Type	Phase 2 FAS INCAGN01876 Population		
3.1.5.1	Summary of Drug Exposure to Nivolumab by Visit - by Treatment Group and Dose	Phase 1 FAS Fixed Nivolumab Population		
3.1.5.2	Summary of Drug Exposure to Nivolumab by Visit - by Treatment Group and Dose	Phase 1 FAS Weighted Nivolumab Population		
3.1.5.3	Summary of Drug Exposure to Nivolumab by Visit - by Treatment Group and Tumor Type	Phase 2 FAS Fixed Nivolumab Population		

Table No.	Title	Population	Standard	In-Text
3.1.5.4	Summary of Drug Exposure to Nivolumab by Visit - by Treatment Group and Tumor Type	Phase 2 FAS Weighted Nivolumab Population		
3.1.6.1	Summary of Drug Exposure to Ipilimumab by Visit - by Treatment Group and Dose	Phase 1 FAS Ipilimumab Population		
3.1.6.2	Summary of Drug Exposure to Ipilimumab by Visit - by Treatment Group and Tumor Type	Phase 2 FAS Ipilimumab Population		
3.2 Adverse Events				
3.2.1.1	Overall Summary of Treatment-Emergent Adverse Events - by Treatment Group and Dose	Phase 1 FAS Population	X	X
3.2.1.2	Overall Summary of Treatment-Emergent Adverse Events - by Treatment Group and Tumor Type	Phase 2 FAS Population	X	X
3.2.2.1	Summary of Treatment-Emergent Adverse Events by MedDRA System Organ Class and Preferred Term - by Treatment Group and Dose	Phase 1 FAS Population	X	
3.2.2.2	Summary of Treatment-Emergent Adverse Events by MedDRA System Organ Class and Preferred Term - by Treatment Group and Tumor Type	Phase 2 FAS Population	X	
3.2.3.1	Summary of Treatment-Emergent Adverse Events by MedDRA Preferred Term in Decreasing Order of Frequency - by Treatment Group and Dose	Phase 1 FAS Population	X	X
3.2.3.2	Summary of Treatment-Emergent Adverse Events by MedDRA Preferred Term in Decreasing Order of Frequency - by Treatment Group and Tumor Type	Phase 2 FAS Population	X	X
3.2.4.1	Summary of Treatment-Emergent Adverse Events by MedDRA System Organ Class, Preferred Term, and Maximum Severity - by Treatment Group and Dose	Phase 1 FAS Population	X	
3.2.4.2	Summary of Treatment-Emergent Adverse Events by MedDRA System Organ Class, Preferred Term, and Maximum Severity - by Treatment Group and Tumor Type	Phase 2 FAS Population	X	
3.2.5.1	Summary of Grade 3 or Higher Treatment-Emergent Adverse Events by MedDRA System Organ Class and Preferred Term - by Treatment Group and Dose	Phase 1 FAS Population	X	X
3.2.5.2	Summary of Grade 3 or Higher Treatment-Emergent Adverse Events by MedDRA System Organ Class and Preferred Term - by Treatment Group and Tumor Type	Phase 2 FAS Population	X	X
3.2.6.1	Summary of Any INCAGN01876 Treatment-Related Adverse Events by MedDRA System Organ Class and Preferred Term - by Treatment Group and Dose	Phase 1 FAS Population	X	X
3.2.6.2	Summary of Any INCAGN01876 Treatment-Related Adverse Events by MedDRA System Organ Class and Preferred Term - by Treatment Group and Tumor Type	Phase 2 FAS Population	X	X
3.2.6.3	Summary of Any Nivolumab Treatment-Related Adverse Events by MedDRA System Organ Class and Preferred Term - by Treatment Group and Dose	Phase 1 FAS Nivolumab Population	X	X

Table No.	Title	Population	Standard	In-Text
3.2.6.4	Summary of Any Nivolumab Treatment-Related Adverse Events by MedDRA System Organ Class and Preferred Term - by Treatment Group and Tumor Type	Phase 2 FAS Nivolumab Population	X	X
3.2.6.5	Summary of Any Ipilimumab Treatment-Related Adverse Events by MedDRA System Organ Class and Preferred Term - by Treatment Group and Dose	Phase 1 FAS Ipilimumab Population	X	X
3.2.6.6	Summary of Any Ipilimumab Treatment-Related Adverse Events by MedDRA System Organ Class and Preferred Term - by Treatment Group and Tumor Type	Phase 2 FAS Ipilimumab Population	X	X
3.2.7.1	Summary of Any Grade 3 or Higher INCAGN01876 Treatment-Related Adverse Events by MedDRA System Organ Class and Preferred Term - by Treatment Group and Dose	Phase 1 FAS Population	X	
3.2.7.2	Summary of Any Grade 3 or Higher INCAGN01876 Treatment-Related Adverse Events by MedDRA System Organ Class and Preferred Term - by Treatment Group and Tumor Type	Phase 2 FAS Population	X	
3.2.7.3	Summary of Any Grade 3 or Higher Nivolumab Treatment-Related Adverse Events by MedDRA System Organ Class and Preferred Term - by Treatment Group and Dose	Phase 1 FAS Nivolumab Population	X	
3.2.7.4	Summary of Any Grade 3 or Higher Nivolumab Treatment-Related Adverse Events by MedDRA System Organ Class and Preferred Term - by Treatment Group and Tumor Type	Phase 2 FAS Nivolumab Population	X	
3.2.7.5	Summary of Any Grade 3 or Higher Ipilimumab Treatment-Related Adverse Events by MedDRA System Organ Class and Preferred Term - by Treatment Group and Dose	Phase 1 FAS Ipilimumab Population	X	
3.2.7.6	Summary of Any Grade 3 or Higher Ipilimumab Treatment-Related Adverse Events by MedDRA System Organ Class and Preferred Term - by Treatment Group and Tumor Type	Phase 2 FAS Ipilimumab Population	X	
3.2.8.1	Summary of Any INCAGN01876 Treatment-Related Adverse Events With a Fatal Outcome by MedDRA System Organ Class and Preferred Term - by Treatment Group and Dose	Phase 1 FAS Population	X	
3.2.8.2	Summary of Any INCAGN01876 Treatment-Related Adverse Events With a Fatal Outcome by MedDRA System Organ Class and Preferred Term - by Treatment Group and Tumor Type	Phase 2 FAS Population	X	
3.2.8.3	Summary of Any Nivolumab Treatment-Related Adverse Events With a Fatal Outcome by MedDRA System Organ Class and Preferred Term - by Treatment Group and Dose	Phase 1 FAS Nivolumab Population	X	
3.2.8.4	Summary of Any Nivolumab Treatment-Related Adverse Events With a Fatal Outcome by MedDRA System Organ Class and Preferred Term - by Treatment Group and Tumor Type	Phase 2 FAS Nivolumab Population	X	

Table No.	Title	Population	Standard	In-Text
3.2.8.5	Summary of Any Ipilimumab Treatment-Related Adverse Events With a Fatal Outcome by MedDRA System Organ Class and Preferred Term - by Treatment Group and Dose	Phase 1 FAS Ipilimumab Population	X	
3.2.8.6	Summary of Any Ipilimumab Treatment-Related Adverse Events With a Fatal Outcome by MedDRA System Organ Class and Preferred Term - by Treatment Group and Tumor Type	Phase 2 FAS Ipilimumab Population	X	
3.2.9.1	Summary of Serious Treatment-Emergent Adverse Events by MedDRA System Organ Class and Preferred Term - by Treatment Group and Dose	Phase 1 FAS Population	X	
3.2.9.2	Summary of Serious Treatment-Emergent Adverse Events by MedDRA System Organ Class and Preferred Term - by Treatment Group and Tumor Type	Phase 2 FAS Population	X	
3.2.10.1	Summary of Serious Treatment-Emergent Adverse Events by MedDRA Preferred Term in Decreasing Order of Frequency - by Treatment Group and Dose	Phase 1 FAS Population	X	X
3.2.10.2	Summary of Serious Treatment-Emergent Adverse Events by MedDRA Preferred Term in Decreasing Order of Frequency - by Treatment Group and Tumor Type	Phase 2 FAS Population	X	X
3.2.11.1	Summary of INCAGN01876 Treatment-Related Serious Treatment-Emergent Adverse Events by MedDRA System Organ Class and Preferred Term - by Treatment Group and Dose	Phase 1 FAS Population	X	
3.2.11.2	Summary of INCAGN01876 Treatment-Related Serious Treatment-Emergent Adverse Events by MedDRA System Organ Class and Preferred Term - by Treatment Group and Tumor Type	Phase 2 FAS Population	X	
3.2.11.3	Summary of Nivolumab Treatment-Related Serious Treatment-Emergent Adverse Events by MedDRA System Organ Class and Preferred Term - by Treatment Group and Dose	Phase 1 FAS Population	X	
3.2.11.4	Summary of Nivolumab Treatment-Related Serious Treatment-Emergent Adverse Events by MedDRA System Organ Class and Preferred Term - by Treatment Group and Tumor Type	Phase 2 FAS Population	X	
3.2.11.5	Summary of Ipilimumab Treatment-Related Serious Treatment-Emergent Adverse Events by MedDRA System Organ Class and Preferred Term - by Treatment Group and Dose	Phase 1 FAS Population	X	
3.2.11.6	Summary of Ipilimumab Treatment-Related Serious Treatment-Emergent Adverse Events by MedDRA System Organ Class and Preferred Term - by Treatment Group and Tumor Type	Phase 2 FAS Population	X	
3.2.12.1	Summary of Non-Serious Treatment-Emergent Adverse Events by MedDRA System Organ Class and Preferred Term - by Treatment Group and Dose	Phase 1 FAS Population	X	
3.2.12.2	Summary of Non-Serious Treatment-Emergent Adverse Events by MedDRA System Organ Class and Preferred Term - by Treatment Group and Tumor Type	Phase 2 FAS Population	X	

Table No.	Title	Population	Standard	In-Text
3.2.13.1	Summary of Treatment-Emergent Adverse Events Leading to INCAGN01876 Dose Reduction by MedDRA System Organ Class and Preferred Term - by Treatment Group and Dose	Phase 1 FAS Population	X	
3.2.13.2	Summary of Treatment-Emergent Adverse Events Leading to INCAGN01876 Dose Reduction by MedDRA System Organ Class and Preferred Term - by Treatment Group and Tumor Type	Phase 2 FAS Population	X	
3.2.14.1	Summary of Treatment-Emergent Adverse Events Leading to Any Dose Interruption by MedDRA System Organ Class and Preferred Term - by Treatment Group and Dose	Phase 1 FAS Population	X	
3.2.14.2	Summary of Treatment-Emergent Adverse Events Leading to Any Dose Interruption by MedDRA System Organ Class and Preferred Term - by Treatment Group and Tumor Type	Phase 2 FAS Population	X	
3.2.15.1	Summary of Treatment-Emergent Adverse Events Leading to Discontinuation of INCAGN01876 by MedDRA System Organ Class and Preferred Term - by Treatment Group and Dose	Phase 1 FAS Population	X	
3.2.15.2	Summary of Treatment-Emergent Adverse Events Leading to Discontinuation of INCAGN01876 by MedDRA System Organ Class and Preferred Term - by Treatment Group and Tumor Type	Phase 2 FAS Population	X	
3.2.16.1	Summary of Treatment-Emergent Immune-Related Adverse Events (Investigator Identified) by MedDRA System Organ Class and Preferred Term - by Treatment Group and Dose	Phase 1 FAS Population	X	
3.2.16.2	Summary of Treatment-Emergent Immune-Related Adverse Events (Investigator Identified) by MedDRA System Organ Class and Preferred Term - by Treatment Group and Tumor Type	Phase 2 FAS Population	X	
3.2.17.1	Summary of Treatment-Emergent Immune-Related Adverse Events (Sponsor Identified) by MedDRA System Organ Class and Preferred Term - by Treatment Group and Dose	Phase 1 FAS Population	X	
3.2.17.2	Summary of Treatment-Emergent Immune-Related Adverse Events (Sponsor Identified) by MedDRA System Organ Class and Preferred Term - by Treatment Group and Tumor Type	Phase 2 FAS Population	X	
3.2.18.1	Summary of Treatment-Emergent Immune-Related Adverse Events (Investigator Identified) by MedDRA System Organ Class, Preferred Term, and Maximum Severity - by Treatment Group and Dose	Phase 1 FAS Population	X	
3.2.18.2	Summary of Treatment-Emergent Immune-Related Adverse Events (Investigator Identified) by MedDRA System Organ Class, Preferred Term, and Maximum Severity - by Treatment Group and Tumor Type	Phase 2 FAS Population	X	

Table No.	Title	Population	Standard	In-Text
3.2.19.1	Summary of Grade 3 or Higher Treatment-Emergent Immune-Related Adverse Events (Investigator Identified) by MedDRA System Organ Class and Preferred Term - by Treatment Group and Dose	Phase 1 FAS Population	X	X
3.2.19.2	Summary of Grade 3 or Higher Treatment-Emergent Immune-Related Adverse Events (Investigator Identified) by MedDRA System Organ Class and Preferred Term - by Treatment Group and Tumor Type	Phase 2 FAS Population	X	X
3.2.20	Life Table Estimate of Time to First Grade 3 or Higher Treatment-Emergent Adverse Event - by Treatment Group and Tumor Type	Phase 2 FAS Population	X	
3.2.21.1	Summary of Adverse Events With a Fatal Outcome by System Organ Class and Preferred Term - by Treatment Group and Dose	Phase 1 FAS Population	X	
3.2.21.2	Summary of Adverse Events With a Fatal Outcome by System Organ Class and Preferred Term - by Treatment Group and Tumor Type	Phase 2 FAS Population	X	
3.2.22.1	Summary of Infusion Reactions - by Treatment Group and Dose	Phase 1 FAS Population		
3.2.22.2	Summary of Infusion Reactions - by Treatment Group and Tumor Type	Phase 2 FAS Population		
3.3 Laboratory				
3.3.1	Summary of Laboratory Values - Hematology	Phase 2 FAS Population	X	
3.3.2.1	Summary of Treatment Emergent Worsening Hematology Laboratory Values in CTC Grade - To the Worst Abnormal Value	Phase 1 FAS Population	X	
3.3.2.2	Summary of Treatment Emergent Worsening Hematology Laboratory Values in CTC Grade - To the Worst Abnormal Value	Phase 2 FAS Population	X	
3.3.3	Summary of Laboratory Values - Chemistry	Phase 2 FAS Population	X	
3.3.4.1	Summary of Treatment Emergent Worsening Chemistry Laboratory Values in CTC Grade - To the Worst Abnormal Value	Phase 1 FAS Population	X	
3.3.4.2	Summary of Treatment Emergent Worsening Chemistry Laboratory Values in CTC Grade - To the Worst Abnormal Value	Phase 2 FAS Population	X	
3.4 Vital Signs				
3.4.1.1	Summary of Systolic Blood Pressure (mmHg)	Phase 1 FAS Population	X	
3.4.1.2	Summary of Systolic Blood Pressure (mmHg) - by Tumor Type	Phase 2 FAS Population	X	
3.4.2.1	Summary of Diastolic Blood Pressure (mmHg)	Phase 1 FAS Population	X	
3.4.2.2	Summary of Diastolic Blood Pressure (mmHg) - by Tumor Type	Phase 2 FAS Population	X	
3.4.3.1	Summary of Pulse (bpm)	Phase 1 FAS Population	X	

Table No.	Title	Population	Standard	In-Text
3.4.3.2	Summary of Pulse (bpm) - by Tumor Type	Phase 2 FAS Population	X	
3.4.4.1	Summary of Respiration Rate (bpm)	Phase 1 FAS Population	X	
3.4.4.2	Summary of Respiration Rate (bpm) - by Tumor Type	Phase 2 FAS Population	X	
3.4.5.1	Summary of Body Temperature (°C)	Phase 1 FAS Population	X	
3.4.5.2	Summary of Body Temperature (°C) - by Tumor Type	Phase 2 FAS Population	X	
3.4.6.1	Summary of Weight (kg)	Phase 1 FAS Population	X	
3.4.6.2	Summary of Weight (kg) - by Tumor Type	Phase 2 FAS Population	X	
3.5 ECG				
3.5.1.1	Summary of PR Interval (msec) From Local Lab 12-Lead ECG	Phase 1 FAS Population	X	
3.5.1.2	Summary of PR Interval (msec) From Local Lab 12-Lead ECG - by Tumor Type	Phase 2 FAS Population	X	
3.5.2.1	Summary of RR Interval (msec) From Local Lab 12-Lead ECG	Phase 1 FAS Population	X	
3.5.2.2	Summary of RR Interval (msec) From Local Lab 12-Lead ECG - by Tumor Type	Phase 2 FAS Population	X	
3.5.3.1	Summary of QT Interval (msec) From Local Lab 12-Lead ECG	Phase 1 FAS Population	X	
3.5.3.2	Summary of QT Interval (msec) From Local Lab 12-Lead ECG - by Tumor Type	Phase 2 FAS Population	X	
3.5.4.1	Summary of QRS Interval (msec) From Local Lab 12-Lead ECG	Phase 1 FAS Population	X	
3.5.4.2	Summary of QRS Interval (msec) From Local Lab 12-Lead ECG - by Tumor Type	Phase 2 FAS Population	X	
3.5.5.1	Summary of QTcB Interval (msec) From Local Lab 12-Lead ECG	Phase 1 FAS Population	X	
3.5.5.2	Summary of QTcB Interval (msec) From Local Lab 12-Lead ECG - by Tumor Type	Phase 2 FAS Population	X	
3.5.6.1	Summary of QTcF Interval (msec) From Local Lab 12-Lead ECG	Phase 1 FAS Population	X	
3.5.6.2	Summary of QTcF Interval (msec) From Local Lab 12-Lead ECG- by Tumor Type	Phase 2 FAS Population	X	
3.5.7.1	Summary of JTc Interval (msec) From Local Lab 12-Lead ECG	Phase 1 FAS Population		
3.5.7.2	Summary of JTc Interval (msec) From Local Lab 12-Lead ECG- by Tumor Type	Phase 2 FAS Population	X	
3.5.8.1	Summary of Heart Rate (beats/min) From Local Lab 12-Lead ECG	Phase 1 FAS Population	X	
3.5.8.2	Summary of Heart Rate (beats/min) From Local Lab 12-Lead ECG - by Tumor Type	Phase 2 FAS Population	X	

Table No.	Title	Population	Standard	In-Text
3.5.9.1	Summary of Alert Values of PR, QRS, QT, RR, and QTcF Interval Values From Local Lab 12-Lead ECG by Visit - by Treatment Group and Dose	Phase 1 FAS Population	X	X
3.5.9.2	Summary of Alert Values of PR, QRS, QT, RR, and QTcF Interval Values From Local Lab 12-Lead ECG by Visit - by Treatment Group and Tumor Type	Phase 2 FAS Population	X	X

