^c As of Protocol Amendment 5, the safety follow-up visits will include AE and concomitant medication assessment only and may be completed remotely (such as by televisit).

- ^d As of Protocol Amendment 5, no further survival follow-up assessment will be required beyond the last safety follow-up visit.
- ^e Evaluation window only applies to Cycle 6 Day 1.
- ^f In Treatment Group B, INCAGN01876 is only administered on Day 1 of Cycles 1 and 2.
- ^g In Treatment Groups B, E, H, and L, nivolumab administration begins at Cycle 3 Day 1.
- ^h For subjects enrolled into Treatment Groups C and C2 (INCAGN01876 + ipilimumab) and Treatment Groups D and J (INCAGN01876 + nivolumab + ipilimumab), ipilimumab will be administered on Cycle 1 Day 1 and then Day 1 of every 3rd cycle (Cycle 1, Cycle 4, Cycle 7, etc). In Treatment Groups E and L ipilimumab administration begins at Cycle 3 Day 1 and then continues on Day 1 of every third cycle. If higher doses of ipilimumab are tested (eg, 3 mg/kg every 3 weeks [21 days] for 4 doses), then ipilimumab will be administered on Day 1 of each 3-week (21-day) cycle for a total of 4 doses. If the scheduled ipilimumab doses fall on days other than Day 1 of a cycle, the subjects will need to be present in clinic for the infusion, and any standard procedures required by the site should be performed.
- ⁱ Applicable to all subjects at Cycle 1 Day 8. At Cycle 6 Day 8, only required if subject is experiencing AEs > Grade 2.
- ^j All 12-lead ECGs will be performed with the subject in a recumbent or semirecumbent position after 5 minutes of rest and should not be performed within 15 minutes after a blood collection. ECGs will be collected at screening and at least every 8 weeks, or as clinically indicated per prescribing instructions for nivolumab, as well as the EOT and first safety follow-up visits.
- ^k The initial tumor imaging will be performed within 28 days before the first dose of study treatment. Images of the chest, abdomen, and pelvis are required for all subjects. Scans performed as part of routine clinical management are acceptable for use as the screening scan if they are of diagnostic quality and performed within 28 days before the first dose of study treatment. The same imaging technique should be used for a subject throughout the study. Local reading (investigator assessment with site radiology reading) will be used to determine eligibility and for subject management.

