### **5.3. Analysis Populations**

#### **5.3.1. Full Analysis Set**

The FAS includes all subjects enrolled in the study who received at least 1 dose of INCAGN01876, nivolumab, or ipilimumab. The FAS will be used for the summary of demographics, baseline characteristics, subject disposition, safety, study treatment administration, and analyses of all efficacy data.

- **Phase 1 FAS Population**

The Phase 1 FAS population includes all subjects in the FAS population who are enrolled in the Phase 1 portion of the study and received at least 1 dose of INCAGN01876, nivolumab, or ipilimumab.

- **Phase 1 FAS INCAGN01876 Population**

The Phase 1 FAS population includes all subjects in the FAS population who are enrolled in the Phase 1 portion of the study and received at least 1 dose of INCAGN01876.

- **Phase 1 FAS Weighted Nivolumab Population**

The Phase 1 FAS weighted nivolumab population includes all subjects in the FAS population who are enrolled in the Phase 1 portion of the study and received at least 1 dose of nivolumab administered in mg/kg. This includes subjects enrolled into Treatment Groups D and E.

- **Phase 1 FAS Fixed Nivolumab Population**

The Phase 1 FAS fixed nivolumab population includes all subjects in the FAS population who are enrolled in the Phase 1 portion of the study and received at least 1 dose of nivolumab administered in mg. This includes subjects enrolled into Treatment Groups A and B.

- **Phase 1 FAS Ipilimumab Population**

The Phase 1 FAS ipilimumab population includes all subjects in the FAS population who are enrolled in the Phase 1 portion of the study and received at least 1 dose of ipilimumab.

- **Phase 2 FAS Population**

The Phase 2 FAS population includes all subjects in the FAS population enrolled in Phase 2 of the study who received at least 1 dose of INCAGN01876, nivolumab, or ipilimumab.

Specific analysis populations to be used for evaluating the Simon 2-stage efficacy rules include the following subgroups:

- Treatment Group F adenocarcinoma of the endometrium
- Treatment Group F with gastric cancer
- Treatment Group F with SCCHN cancer
- Treatment Group G with adenocarcinoma of the endometrium
- Treatment Group G with gastric cancer
- Treatment Group G with SCCHN cancer
- Treatment Group H with adenocarcinoma of the endometrium
- Treatment Group H with gastric cancer
- Treatment Group H with SCCHN cancer
- Treatment Group J with adenocarcinoma of the endometrium
- Treatment Group J with gastric cancer

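### Four drug-attributed serious-AE tables (SAP Appendix A, 3.2.11.3 to 3.2.11.6) use the whole FAS, while the twelve matching tables use only subjects exposed to that drug

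*SAP*

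**What the plan says.** The table list in SAP Appendix A gives a population for each planned table. For serious events attributed to a partner drug, the four entries, title followed by population, are:

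- Table 3.2.11.3: "Nivolumab Treatment-Related Serious Treatment-Emergent Adverse Events by MedDRA System Organ Class and Preferred Term - by Treatment Group and Dose Phase 1 FAS Population"
- Table 3.2.11.4: "Nivolumab Treatment-Related Serious Treatment-Emergent Adverse Events by MedDRA System Organ Class and Preferred Term - by Treatment Group and Tumor Type Phase 2 FAS Population"
- Table 3.2.11.5: "Ipilimumab Treatment-Related Serious Treatment-Emergent Adverse Events by MedDRA System Organ Class and Preferred Term - by Treatment Group and Dose Phase 1 FAS Population"
- Table 3.2.11.6: "Ipilimumab Treatment-Related Serious Treatment-Emergent Adverse Events by MedDRA System Organ Class and Preferred Term - by Treatment Group and Tumor Type Phase 2 FAS Population"

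The corresponding tables for any related event, Grade 3 or higher related events and fatal related events name a drug-specific population instead. In Phase 1 these are "Phase 1 FAS Nivolumab Population" and "Phase 1 FAS Ipilimumab Population", with the Phase 2 equivalents in the Phase 2 rows.

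SAP 5.3.1 sets the wider population: "The FAS includes all subjects enrolled in the study who received at least 1 dose of INCAGN01876, nivolumab, or ipilimumab". The protocol's schedule of clinical assessments (Table 10, footnotes) states: "In Treatment Groups B, E, H, and L, nivolumab administration begins at Cycle 3 Day 1". The same footnotes start ipilimumab at Cycle 3 Day 1 in Groups E and L. SAP 8.2.5 lists the serious related-event summaries without naming a population.

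**The concern.** A table of events attributed to one drug describes the subjects who were at risk from that drug. In a run-in group, a subject who leaves during the two INCAGN01876-only cycles is in the FAS but has never received nivolumab or, in the triplets, ipilimumab. Counting that subject lowers the serious related rate for a drug that the subject did not take.

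The second problem is consistency within the report. One event can be nivolumab-related, Grade 3 or higher, and serious. It would then be shown over the exposed subjects in Table 3.2.7.3 or 3.2.7.4 and over the whole FAS in Table 3.2.11.3 or 3.2.11.4, for the same treatment group. A reader who sets the two side by side would not be comparing like with like. Adverse-event frequency is part of the primary safety endpoint, so the denominators should be chosen on purpose and stated.

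**Working it through.** The plan states no figure to reproduce. The check compares the population entries and then sizes the effect.

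**1. Population by event class (SAP Appendix A)**

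| Related events | Nivolumab tables | Ipilimumab tables | Population named |
|---|---|---|---|
| Any | 3.2.6.3, 3.2.6.4 | 3.2.6.5, 3.2.6.6 | Drug-specific FAS |
| Grade 3 or higher | 3.2.7.3, 3.2.7.4 | 3.2.7.5, 3.2.7.6 | Drug-specific FAS |
| Fatal | 3.2.8.3, 3.2.8.4 | 3.2.8.5, 3.2.8.6 | Drug-specific FAS |
| Serious | 3.2.11.3, 3.2.11.4 | 3.2.11.5, 3.2.11.6 | Plain FAS |

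All twelve rows in the first three classes are drug-specific, and all four serious rows are not.

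**2. Who is in the FAS without exposure.** Cycles last 14 days, so the run-in covers the first two cycles (28 days). For nivolumab the groups concerned are B, E, H and L; for ipilimumab, E and L. The SAP also has run-in groups G (nivolumab) and K (both drugs), which the current protocol's Phase 2 group table no longer lists. In the concurrent groups the partner drug is scheduled on Cycle 1 Day 1, so the FAS and the exposed set nearly coincide.

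**3. Size.** Let d be the share of a run-in group's FAS that never reaches Cycle 3 Day 1. If unexposed subjects contribute no events,

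rate on FAS = rate among exposed × (1 − d).

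The relative reduction is d. Neither d nor the rate is in the documents. With an assumed 15% rate among the exposed:

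- d = 0: 15.0%
- d = 5%: 0.15 × 0.95 = 14.25%, about 14.3%
- d = 10%: 0.15 × 0.90 = 13.5%
- d = 20%: 0.15 × 0.80 = 12.0%
- d = 30%: 0.15 × 0.70 = 10.5%

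In counts, take a group of 50 with 10 never exposed and 5 subjects with an event. The rate is 5/50 = 10.0% on the FAS and 5/40 = 12.5% among the exposed.

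**4. Limits of the formula.** SAP 8.2.1 treats unresolved missing causality as treatment-related. An unexposed subject could therefore enter a drug-related count, and the identity in step 3 need not hold exactly. Groups never assigned the drug (C, and C2 in the protocol, for nivolumab; A, B, F and H, and G in the SAP, for ipilimumab) have no exposed subjects. They appear as structural-zero columns and leave the other groups' columns unchanged.

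**The case against.** The case for leaving the tables alone has some weight.

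- SAP 5.3.1 names the FAS as the general population for safety, and the neighbouring all-cause serious tables (3.2.9 and 3.2.10) use it. This does not settle the matter, because Appendix A departs from that default in all twelve matching rows.
- The SAP is not otherwise uniform. The overall AE summary in SAP 8.2.5 includes lines for nivolumab-related and ipilimumab-related TEAEs, and Tables 3.2.1.1 and 3.2.1.2 are on the FAS. This stands, and it means that correcting only the four tables would leave the same mismatch there.
- No decision rests on these tables. They are not marked as in-text, and the Phase 2 enrollment-interruption rule in SAP 3.2 uses Grade 3 to 5 INCAGN01876-related events. This stands.
- Appendix A describes its table list as a guideline. That makes the correction easy; it does not remove the conflict.
- The share d is unknown and may be small. This stands.

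A reader might infer that run-in dosing would look safer than concurrent dosing purely through the arithmetic. The documents do not support going that far. The study is nonrandomized, and protocol Section 4.2 limits comparisons to pretreatment conditions. An exposed-only denominator also selects subjects who stayed on treatment to Cycle 3, so it would not make the schedules comparable either. A reader might also want to restrict these tables to events that begin on or after the first dose of the drug in question. SAP 8.2.1 defines treatment emergence from the first dose of study treatment, and no drug-specific onset rule is stated for the matching tables. Adding one here would create a new inconsistency.

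**Conclusion.** The point holds as a minor but real inconsistency. Followed as written, the plan puts subjects who never received nivolumab or ipilimumab into the denominator of a serious-event rate attributed to that drug. It also gives that rate a different denominator from the any-grade, Grade 3 or higher and fatal tables. The within-group effect falls mainly on the run-in groups, and its relative size is d: none at d = 0, and 5% to 30% for the assumed range of d. These sizes rest on an assumed d, an assumed 15% rate and no events attributed to the drug in unexposed subjects. The all-cause and INCAGN01876-related serious tables, the stopping rules and the efficacy results are not affected.

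**What to change.** 1. Define a Phase 1 and a Phase 2 FAS Nivolumab Population in SAP 5.3.1: subjects in that phase with at least one dose of nivolumab, which is the union of the Weighted and Fixed nivolumab populations. The section now defines only those two, so the name already used in Tables 3.2.6 to 3.2.8 has no definition. The ipilimumab populations are already defined.
2. Assign Tables 3.2.11.3 and 3.2.11.4 to the Phase 1 and Phase 2 FAS Nivolumab Population, and Tables 3.2.11.5 and 3.2.11.6 to the Phase 1 and Phase 2 FAS Ipilimumab Population.
3. Use the same denominators for the nivolumab- and ipilimumab-related lines of the overall AE summary (Tables 3.2.1.1 and 3.2.1.2), with a footnote stating them.

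The cost is one added definition per phase, four population entries and a denominator change in two summary tables, with no new data. The downside is slightly smaller denominators and slightly higher reported rates in the run-in groups.
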